PROTOCOL TITLE: Amlodipine versus nifedipine ER for the management of postpartum hypertension: A randomized controlled noninferiority trial

Lead Investigator:

[name]

Prisma Health/University of South Carolina Greenville

Version Date: August 8, 2022

TABLE OF CONTENTS

Table of contents.....	2
Protocol Synopsis.....	3
1 BACKGROUND AND RATIONALE.....	5
2 STUDY OBJECTIVES.....	7
3 INVESTIGATIONAL PLAN.....	8
4 STUDY PROCEDURES.....	9
5 STUDY EVALUATIONS AND MEASUREMENTS.....	12
6 STATISTICAL CONSIDERATIONS.....	13
7 DATA COLLECTION AND MANAGEMENT.....	13
8 REFERENCES.....	13

PROTOCOL SYNOPSIS

Study Title	Amlodipine versus nifedipine ER for the management of postpartum hypertension: A randomized controlled noninferiority trial
Funder	Prisma Health OBGYN Departmental Research Fund
Study Rationale	
-A significant number of pregnancies are complicated by hypertensive disorders (chronic hypertension, gestational hypertension, preeclampsia)-Hypertension is often exacerbated in the postpartum period-Many of these patients require initiation of antihypertensives after delivery-There are a limited number of well-studied treatment options routinely used (labetalol and nifedipine ER)-Prior studies have shown that both labetalol and nifedipine ER are effective-Nifedipine ER has few contraindications, but has significantly more side effects than labetalol-Headache is one of the most commonly reported side effects with nifedipine ER-Headache is also a commonly reported symptom of preeclampsia-Amlodipine is in the same drug class as nifedipine ER, but does not cause headaches-Amlodipine is a first-line antihypertensive in the non-obstetric population-Amlodipine has not been studied in the obstetric population
Study Objectives	
Primary
 
-To evaluate whether amlodipine is noninferior to nifedipine ER in the management of postpartum hypertension 
Secondary
 
-To evaluate whether patients tolerate amlodipine better than nifedipine ER
Study Design	Unmasked, pragmatic randomized controlled trial

Subject Population Inclusion criteria

- English and Spanish-speaking postpartum women with a diagnosis of chronic hypertension, gestational hypertension, or preeclampsia
- Delivery at or beyond 20 weeks' gestation
- Need for antihypertensive therapy, defined as blood pressure $>/= 150$ mmHg systolic and/or 100 mmHg diastolic on two occasions four hours apart, or one severe blood pressure >160 mmHg systolic and/or 110 mmHg diastolic.
- Age 18 years or older

Exclusion criteria

- Use of antihypertensives prior to delivery (either for hypertension or other indications, i.e. tachycardia)
- Allergy to nifedipine ER or amlodipine
- Persistent tachycardia (as defined by the treatment team)

Number of Subjects 160

Study Duration Each subject's participation is expected to last less than 8 weeks
The entire study is expected to last 24 months

Study phases

- Screening: Women admitted to Greenville Memorial Hospital Family Birthplace will be screened on admission to determine if they have a hypertension diagnosis. Additionally, postpartum women on the Women's Specialty unit who do not meet criteria prior to delivery will be rescreened once daily. Women with hypertensive diagnoses will be approached about their willingness to participate in the study, either at the time of admission or at time of diagnosis.
- Randomization: Participants will be randomized to either nifedipine ER or amlodipine at the time of enrollment. In order to maximize participant capture, all screened patients who have a hypertensive diagnosis and agree to study participation will be consented and randomized. Only those who progress to needing antihypertensives will meet full inclusion criteria and ultimately be enrolled in the study.
- Intervention: Those participants meeting inclusion criteria for antihypertensives will be administered the study medication. Participants will be administered either amlodipine or nifedipine ER, depending on their treatment arm allocation.

-Follow-up: Data regarding the patient's need for additional medications, side effects, and length of stay will be collected throughout the hospitalization. Patients will attend a blood pressure check visit ideally 3 to 7 days after hospital discharge (virtual (for patients with home blood pressure cuff only) or in-person) and a postpartum visit ideally 4-6 weeks after delivery (in person), per standard of care. Additional data will be collected at these visits.

Safety Evaluations	While hospitalized, patients will be monitored daily by the clinical team to assess for side effects and ensure adequate blood pressure control. Adjustments will be made by the clinical team as indicated based on patient status. After hospital discharge, patients will be able to call the office with any concerns and additional appointments for evaluation can be made as necessary.
Statistical and Analytic Plan	Noninferiority of amlodipine will be assessed with Wilcoxon Rank-Sum

Data and Safety Monitoring Plan	Participants will be provided with contact information for the PI should they have any concerns.
--	--

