2 STUDY OBJECTIVE

2.1 Primary Objective

The primary hypothesis of this study is that amlodipine is noninferior to nifedipine ER in the management of postpartum hypertension, as evidenced by length of stay from delivery until hospital discharge. A noninferiority limit of 24 hours was selected as a clinically relevant difference.

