5 STUDY EVALUATIONS AND MEASUREMENTS

-Demographic characteristics and clinical data will be abstracted from the medical chart

-Maternal age

-Gestational age at delivery

-Race

-BMI

-Parity

-Mode of delivery

-Hypertensive diagnosis

-History of diabetes (gestational or pre-gestational)

-Length of stay from delivery until discharge

-Number of acute antihypertensive treatments

-Number of dose increases of initial study drug

-Number of additional long-acting antihypertensives started

-Magnesium use

-Side effects reported

-Medication discontinuation

-Discharging physician

-Blood pressure at blood pressure check appointment

-Blood pressure at postpartum visit

- Readmissions from time of discharge until postpartum visit
- Breastfeeding status at time of postpartum visit
- Patient-reported length of breastfeeding
- Patient-reported breastfeeding satisfaction

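### The only stated window for side effects is the hospital stay, whose length is the primary outcome, and no side-effect assessment is specified after discharge.

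*Combined protocol and SAP*

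**What the plan says.** Tolerability is the secondary objective in the Protocol Synopsis: "To evaluate whether patients tolerate amlodipine better than nifedipine ER". Section 2.2 names patient-reported side effects, and discontinuation because of them, as secondary outcomes.

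On timing, the Follow-up item under Study phases in the synopsis says "Data regarding the patient's need for additional medications, side effects, and length of stay will be collected throughout the hospitalization". The same item describes a blood pressure check, ideally 3 to 7 days after discharge, and a postpartum visit, ideally 4 to 6 weeks after delivery. Of these it says only "Additional data will be collected at these visits".

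Section 5 lists "Side effects reported" with no time point. Other items in that list are dated, for example "Readmissions from time of discharge until postpartum visit". The items it ties to follow-up are blood pressures, readmissions and breastfeeding.

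The Safety Evaluations row of the synopsis says "While hospitalized, patients will be monitored daily by the clinical team to assess for side effects". After discharge it provides for calls from the patient and extra appointments as needed.

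Section 2.1 sets the primary hypothesis "as evidenced by length of stay from delivery until hospital discharge" and adds "A noninferiority limit of 24 hours was selected as a clinically relevant difference". Under Section 3.1 the trial is unmasked and discharge criteria may vary somewhat between providers.

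**The concern.** The observation time for a secondary outcome is set by the primary outcome. A cumulative count of women with any side effect tends to rise with time observed, and here observation ends at a discharge decided by an unmasked team. If one arm stays longer, part of any difference in side effects may reflect longer observation rather than the drug.

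The distortion works against whichever arm stays longer. A longer amlodipine stay could hide a real tolerability advantage. A longer nifedipine ER stay could exaggerate one, and the noninferiority margin places no limit in that direction. The link may also run the other way: Section 1 notes that headache can alter management, so a side effect could itself affect the stay.

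The second gap is after discharge. Under the present text, asking about side effects at the two visits and not asking would both comply with the protocol. A reader of the results could not tell which period the tolerability comparison covers.

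**Working it through.** **Plan's own figure.** There is none to reproduce. The documents give no sample size, expected rate or analysis for the side-effect comparison. The only sample-size figure concerns length of stay and is not used here.

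**Inputs.**
- From the documents: the 24 h margin (Section 2.1), used as the largest stay difference examined.
- Assumed: a constant reporting rate; a base risk p of 30% (range 20% to 40%) over T = 48 h on drug (also 72 h and 96 h); a stay longer by d = 6, 12 or 24 h. The documents do not give the time from first dose to discharge. That interval is what matters here, and it is no longer than the stay from delivery.

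**Formula.** With a constant rate λ, risk over t hours is 1 − exp(−λt). If risk over T is p, risk over T + d is 1 − (1 − p)^((T + d)/T). For p = 30% and T = 48 h, λ = −ln(0.70)/48 = 0.00743 per hour.

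**Effect of a longer stay alone, with identical drugs.**

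| p over T | T (h) | d (h) | Calculation | Risk | Added points |
|---|---|---|---|---|---|
| 30% | 48 | 0 | no change | 30.0% | 0 |
| 30% | 48 | 6 | 1 − 0.70^1.125 | 33.1% | 3.1 |
| 30% | 48 | 12 | 1 − 0.70^1.25 | 36.0% | 6.0 |
| 30% | 48 | 24 | 1 − 0.70^1.5 | 41.4% | 11.4 |
| 20% | 48 | 24 | 1 − 0.80^1.5 | 28.4% | 8.4 |
| 40% | 48 | 24 | 1 − 0.60^1.5 | 53.5% | 13.5 |
| 30% | 72 | 24 | 1 − 0.70^1.333 | 37.8% | 7.8 |
| 30% | 96 | 24 | 1 − 0.70^1.25 | 36.0% | 6.0 |

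The stay difference drives the result, and longer time on drug reduces it. If every woman who will report a side effect does so before the shorter stay ends, the added risk is zero.

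**Illustration with the rates cited in Section 1** (41% nifedipine ER, 27% amlodipine, a 14-point difference). Suppose these held over T and amlodipine stayed 24 h longer. The observed amlodipine risk would be 1 − 0.73^1.5 = 37.6% at T = 48 h, 34.3% at 72 h and 32.5% at 96 h. The difference would shrink to 3.4, 6.7 or 8.5 points. With 12 h longer it would be 8.5, 10.3 or 11.2 points. These rates come from a non-obstetric study whose observation window the documents do not give, so this shows direction and rough scale only.

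**The case against.** The strongest reply is that the distortion may not arise. Section 1 hypothesizes equivalent times to discharge, and with equal stays it is zero. The 24 h case is extreme, because a true excess that large on amlodipine is the margin itself. This stands as a limit on size. It does not remove the point: equality is not known in advance, and a noninferior result would not exclude a difference of 6 or 12 h.

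A reader might infer that women spend weeks on the drug unobserved after discharge. The documents do not support that. Two visits collect additional data, the side-effect item in Section 5 is undated, and women may call the office or be seen again. Nor do the documents say how long treatment continues after discharge, so the weeks to the postpartum visit are calendar time, not known exposure. What can be said is that no side-effect assessment is specified after discharge.

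It can also be argued that side effects during the admission are a valid randomized comparison of that quantity, and a relevant one, since Section 1 is concerned with drug headache being mistaken for preeclampsia. That is fair. The whole-stay count is worth reporting. It answers a different question from whether women tolerate one drug better over the same time.

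Finally, a constant rate is a simplification. If side effects cluster in the first day or two, the figures above are too high.

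**Conclusion.** The point holds in a conditional form. The one stated side-effect window has a length that can differ by arm, no common window or exposure adjustment is given, and assessment at the two visits is left open. With a constant rate and 30% reporting over 48 h, a longer stay alone adds about 3 points at 6 h, 6 at 12 h and 11 at 24 h. At 24 h the range is 8 to 14 points for a base risk of 20% to 40%.

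A reader might take the 11 points as the expected bias. It is not: it needs a constant rate, 48 h on drug and a stay difference equal to the whole margin. The primary outcome is unaffected. This should be corrected because tolerability is the secondary objective named in the synopsis and the correction is cheap.

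**What to change.** Amend the synopsis and Section 5 as follows.

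- Make the between-arm comparison of side effects over a window common to both arms and counted from first dose, for example the first 24 h.
- Record the same yes/no side-effect items at the existing blood pressure check and at the postpartum visit, and give the Section 5 item these time points.
- Record time since first dose at the blood pressure check. That visit is timed from discharge, so time on drug there still depends on length of stay. The postpartum visit is timed from delivery and does not have this problem.
- Report the whole-stay count descriptively only.

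The cost is a short form at two standard-of-care visits and a few sentences of protocol text. The downside is some missing answers from women who miss a visit.

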1 BACKGROUND AND RATIONALE

Hypertensive disorders of pregnancy are a major cause of maternal morbidity and mortality, and it is felt that at least a portion of these adverse outcomes are preventable¹. Worldwide, between 2 and 8 percent of pregnancies are complicated by preeclampsia². Additionally, 0.9 to 1.5 percent of pregnant women have pre-existing chronic hypertension³. Postpartum hypertension can either be due to an exacerbation of existing chronic hypertension or preeclampsia, or it can be new onset^{2,4}. Blood pressures tend to increase in the postpartum period, peaking at three to six days postpartum. It is not uncommon for women who did not require medications during the pregnancy to be started on an antihypertensive in the postpartum period^{3,5}. If blood pressures are greater than or equal to 150 mmHg systolic and/or 100 mmHg diastolic on two occasions four to six hours apart, antihypertensive therapy is recommended^{4,6,7}.

The most commonly used antihypertensive medications in the postpartum period are labetalol and nifedipine ER. Studies have shown that nifedipine ER is at least as effective, and potentially even more effective, than labetalol in achieving blood pressure control^{4,7}. However, significantly more patients have side effects when taking nifedipine ER (48% versus 20%), and 24% of women using nifedipine ER report headache as a side effect⁷. Headache is a known symptom of preeclampsia, and its presence as a symptom can change patient management. When patients are using nifedipine ER, it can be difficult to determine if the headache is due to the medication or the disease, making management decisions difficult.

Like nifedipine ER, amlodipine is a dihydropyridine calcium channel blocker⁸. Headache is not a commonly reported side effect of amlodipine. Amlodipine is not commonly used in the postpartum setting, but a prior study in the non-obstetrical population demonstrated that amlodipine and nifedipine ER resulted in comparable reductions in blood pressure and can be considered equivalent. Amlodipine was also found to have a significantly lower rate of side effects than nifedipine ER (27% versus 41%)⁹.

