2.2 Secondary Objective

Secondary outcomes include the need for additional antihypertensive medications (either increased dose, additional long-acting agents, or additional short-acting agents), patient-

reported side effects, medication discontinuation due to side effects, hospital readmissions, duration of breastfeeding, and breastfeeding continuation and satisfaction.

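### The only window given for additional antihypertensives is the hospital stay, and no medication item is named for the visits after discharge

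*Combined protocol and SAP*

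**What the plan says.** Section 2.2 lists among the secondary outcomes the "need for additional antihypertensive medications (either increased dose, additional long-acting agents, or additional short-acting agents". It gives no start or end of counting.

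The synopsis (Study phases, Follow-up) supplies the only window: data on the "need for additional medications, side effects, and length of stay will be collected throughout the hospitalization". After describing the blood pressure check and the postpartum visit, it adds: "Additional data will be collected at these visits". It does not name the items.

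Section 5 is the only itemised data list. Its escalation items, such as "Number of acute antihypertensive treatments" and "Number of dose increases of initial study drug", carry no dates, and nor does the item for added long-acting agents. The items it ties to the period after discharge are "Blood pressure at blood pressure check appointment", blood pressure at the postpartum visit, readmissions up to that visit, and breastfeeding. It has no item for current antihypertensive, dose or change since discharge at either visit.

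Section 1 says: "Blood pressures tend to increase in the postpartum period, peaking at three to six days postpartum". Section 3.1 places the blood pressure check ideally 3 to 7 days after discharge, and section 3.3 runs participation through the postpartum visit. Section 7 says that data are entered from the medical record.

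**The concern.** Need for extra drugs is the outcome that could show whether a similar length of stay reflects similar blood pressure control. Three things weaken it if data are collected as the text reads.

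- **Its window depends on the primary endpoint.** A count that ends at discharge has a length set by length of stay, which is the primary endpoint. The trial is unmasked and discharge criteria vary between providers (section 3.1). If one arm goes home sooner, its women have less time in which an escalation can be counted.
- **Escalation after discharge is not specified for collection.** By the protocol's own background, pressure is highest around days 3 to 6, when some women may already be at home. The synopsis expects that women may call or be seen at extra appointments after discharge, so changes of treatment in that period are foreseeable.
- **Visit pressures lack the treatment behind them.** Similar pressures in the two arms could come from the assigned drugs, or from added drugs in one arm. Without concurrent medication the two cannot be told apart.

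**Working it through.** The plan gives no figure for this outcome, so there is none to reproduce. The sample size in section 6.1 concerns length of stay and does not enter here. The check has two parts.

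**1. Which data items have a stated time**

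| Item | Where listed | Time stated |
|---|---|---|
| Need for additional antihypertensives (outcome) | Section 2.2 | None |
| Need for additional medications (collection) | Synopsis, Follow-up | Hospitalization |
| Acute treatments, dose increases, added long-acting agents | Section 5 | None |
| Blood pressure | Section 5 | Both visits after discharge |
| Readmissions | Section 5 | Discharge to postpartum visit |
| Breastfeeding status | Section 5 | Postpartum visit |
| Current drug, dose, change since discharge | Not listed | – |

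Section 5 dates several items after discharge, but not the escalation items. Read with the synopsis, the natural meaning is that escalation is counted in hospital. That is an inference. No sentence excludes later collection, and none provides for it.

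**2. How much of the peak falls inside the hospital stay**

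Inputs:
- Peak at three to six days postpartum (section 1), taken as 72 to 144 h after delivery, a span of 72 h.
- Discharge time D in hours after delivery. The documents give no mean or median stay, so D is assumed and varied.

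Formula: share of the peak window spent in hospital = max(0, min(D, 144) − 72) / 72.

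| Assumed discharge D | Overlap | Share of peak window |
|---|---|---|
| 48 h | 0 h | 0% |
| 72 h | 0 h | 0% |
| 96 h | 96 − 72 = 24 h | 24/72 = 33% |
| 120 h | 120 − 72 = 48 h | 48/72 = 67% |
| 144 h | 144 − 72 = 72 h | 72/72 = 100% |

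The range has to be this wide. Section 6.1 uses a standard deviation of 55.2 h for length of stay, so stays well beyond 96 h are plausible.

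The check visit can be placed the same way. If discharge is on day 2 to 4 (assumed), a check 3 to 7 days later falls between day 2 + 3 = 5 and day 4 + 7 = 11. For such women, most or all of the peak comes after discharge.

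**The case against.** The strongest reply is that the protocol does not restrict collection to the hospital. The synopsis promises further data at the visits, the section 5 items are undated, and the data source is the medical record, where outpatient changes may be found. Readmissions are captured to the postpartum visit, so the most serious failures of control after discharge are covered. An in-hospital window would also be a defensible choice if it were stated.

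Much of this stands, and it rules out several stronger readings that a reader might infer:

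- **That collection is confined to the stay, or that later escalation is lost.** The text does not say so. Later changes are not specified for collection. They could be recovered from the chart, but only if the form asks for them.
- **That visit blood pressures cannot be interpreted.** They can be compared by assigned arm, which is a valid treatment-policy comparison in a pragmatic trial where added drugs are allowed. What is missing is the means to attribute them to the assigned drug alone. Visit pressure is also a data item in section 5, not a secondary outcome in section 2.2.
- **That the effect must hide a difference.** The direction depends on which arm leaves earlier and which escalates later. Neither is known, and unequal windows can create a difference as well as mask one.
- **That power is lost by a known amount.** Suppose true escalation is 50% versus 30% and half of it follows discharge. The in-hospital count then sees 25% versus 15%, and with 80 per arm (two-sided 0.05, normal approximation) power falls from about 75% to 36%. The arithmetic is right, but the rates and the half are assumed, and halving both rates produces the loss by construction. The plan makes no power claim for this outcome.

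The reply does not remove the core gap. A listed secondary outcome has no defined end of counting, the one window in the text ends at discharge, and no medication item is named for either visit. Even on the mildest reading, staff could abstract to different end dates.

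**Conclusion.** The point holds as a cheap improvement to a secondary outcome. As written, need for additional antihypertensives is counted over a period whose length is set by length of stay, escalation after discharge is not specified for collection, and visit pressures cannot be attributed to the assigned drug alone.

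The direction and size of any bias cannot be derived from the documents. The in-hospital share of the peak window runs from 0% to 100% over assumed discharge times of 48 to 144 h, and rests on reading the peak as 72 to 144 h after delivery. The primary endpoint, length of stay, is unaffected.

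**What to change.** - **Section 2.2:** define need for additional antihypertensives from first study dose through the postpartum visit, with the in-hospital part reported separately. Align the Follow-up text in the synopsis.
- **Section 5:** at the blood pressure check and at the postpartum visit, add current antihypertensives with dose, and any change since discharge (increase, added agent, switch, stop) with its date, abstracted from the record.
- **Reporting:** give visit blood pressure by assigned arm together with the share of women on the assigned drug alone at that visit.

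This changes data collection only, not treatment. The cost is a few REDCap fields at visits that already take place as standard of care. The downside is some missing data in women who skip a visit, so the number with data at each visit should be shown by arm.

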Nifedipine ER is considered safe in breastfeeding women. Typically, a relative infant dose (RID) less than 10% is considered safe, and nifedipine ER has a RID of 2.3%. There is limited data on amlodipine use in breastfeeding women, and therefore the LactMed Database currently recommends an alternative to amlodipine if possible. However, one study has shown that the median RID for amlodipine is 4.18%, suggesting it is safe to use in breastfeeding women. In addition, multiple case reports of breastfeeding mothers using amlodipine did not demonstrate any adverse effects in the infant¹⁰. Although further data should continue to be collected, these prior studies and case reports are reassuring.

We hypothesize that amlodipine will be as effective as nifedipine ER in controlling blood pressures in patients with postpartum hypertension, as reflected by equivalent times from delivery to hospital discharge. In addition, we hypothesize that women taking amlodipine will report fewer side effects than those taking nifedipine ER. No effects on breastfeeding outcomes are expected.

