3.2 Allocation to Treatment Groups and Blinding (if applicable)

A computer-generated randomization schedule with 1:1 allocation will be utilized.

Randomization will occur at time of study enrollment utilizing REDCap. Randomization will be stratified by chronic hypertension diagnosis status. The research staff will be responsible for accessing the centralized randomization system, obtaining patient allocation, and notifying the treatment team of patient assignment.

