3.3 Study Duration, Enrollment, and Number of Subjects

Study duration for each participant will last less than 8 weeks (enrollment during initial hospitalization through postpartum visit). 160 patients will be enrolled. This is anticipated to take approximately 18 months.

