6 STATISTICAL CONSIDERATION

6.1 Sample size calculation

An initial power calculation was performed using a standard deviation of 55.2 hours and a non-inferiority limit of 24 hours; to achieve 80% power with a 2-tailed alpha of 0.05, 66 women would be needed in each arm.

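### The 24-hour limit is not built into the primary test, and no result is defined as noninferior

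*Combined protocol and SAP*

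**What the plan says.** - **Method.** The Statistical and Analytic Plan row of the Protocol Synopsis has one sentence: "Noninferiority of amlodipine will be assessed with Wilcoxon Rank-Sum".
- **Endpoint and limit.** Section 2.1 frames the primary hypothesis as noninferiority, "as evidenced by length of stay from delivery until hospital discharge", and adds: "A noninferiority limit of 24 hours was selected as a clinically relevant difference". It does not say whether the 24 h refers to means, medians or a location shift.
- **Alpha.** It appears only in Section 6.1, which takes a "standard deviation of 55.2 hours and a non-inferiority limit of 24 hours" and states that "to achieve 80% power with a 2-tailed alpha of 0.05, 66 women would be needed in each arm".
- **Rest of Section 6.** There is none; the sample size paragraph is the whole section.

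No section states a null hypothesis containing the limit, a shift of the data by 24 h, a confidence interval and its level, or the result that would establish noninferiority.

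**The concern.** Run in its ordinary form, a rank-sum test has equality of the two arms as its null. A non-significant result is then not evidence of noninferiority, because it may only reflect too little information. A significantly longer stay on amlodipine does not show an excess of 24 h either. Neither outcome answers the question in Section 2.1.

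A rank-sum test can assess noninferiority if one arm is shifted by the limit first, or if the matching confidence limit is compared with 24 h. The choice of a rank method is therefore not the problem. The problem is that the plan does not commit to a rule. The primary conclusion of an unmasked trial rests on this one line, and the same data could be called noninferior or not according to how the line is read once results are known.

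**Working it through.** **1. The plan's own sample size.** Inputs from Section 6.1: SD 55.2 h, limit 24 h, power 80%. True difference 0 h is an assumption, taken from the Section 1 hypothesis of efficacy "as reflected by equivalent times from delivery to hospital discharge". For a comparison of means,

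n per arm = 2 (55.2/24)² (z + 0.8416)² = 10.58 (z + 0.8416)².

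- One-sided 0.05 (z = 1.6449): 65.4, so 66.
- Two-tailed 0.05, that is one-sided 0.025 (z = 1.9600): 83.04, so 84.

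The stated 66 reproduces only at one-sided 0.05. At the stated two-tailed level, power for means is Φ(24 / (55.2 √(2/66)) − 1.96) = Φ(0.538) = 70.5% at 66 per arm, and Φ(0.790) = 78.5% at 80 per arm. Section 6.1 therefore cannot settle whether a 90% or a 95% interval decides the trial.

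**2. Two readings of the analysis line, compared by simulation.**

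- Reading A: success if the ordinary two-sided rank-sum p exceeds 0.05. No document states this rule; it is one possible misreading.
- Reading B: success if the rank-sum test, with the amlodipine arm shifted down by 24 h, rejects at one-sided 0.025.

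Arm sizes are 66 (Section 6.1) and 80. The 80 comes from "160 patients will be enrolled" (Section 3.3) split evenly under the 1:1 allocation of Section 3.2. SD is 55.2 h in both arms and the true effect is a pure location shift. The documents give no control mean, so the lognormal means of 60, 90, 120 and 150 h are assumptions. There were at least 20,000 simulated trials per cell, using the normal approximation with continuity correction. Entries are percentages at 66 / 80 per arm.

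| Stays | A passes, true excess 24 h | B passes, true excess 24 h | A passes but B fails, no difference | Power of B, no difference |
|---|---|---|---|---|
| Normal | 32.3 / 23.8 | 2.4 / 2.5 | 30.2 / 21.5 | 67.9 / 75.9 |
| Lognormal, mean 60 h | 1.7 / 0.5 | 2.6 / 2.3 | 0.4 / 0.03 | 98.4 / 99.5 |
| Lognormal, mean 90 h | 10.0 / 5.1 | 2.4 / 2.5 | 7.2 / 2.9 | 90.5 / 94.7 |
| Lognormal, mean 120 h | 17.5 / 10.5 | 2.4 / 2.3 | 14.9 / 8.5 | 82.6 / 89.0 |
| Lognormal, mean 150 h | 22.2 / 15.2 | 2.2 / 2.4 | 19.9 / 12.1 | 77.5 / 85.6 |

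A consistency check: swapping the arms turns reading A at a 24 h excess into reading B at no difference, so the first column should be close to 100 minus the last. For normal data at 66 per arm, 100 − 67.9 = 32.1, against 32.3.

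**3. Interval form of B.** The rule that the Hodges-Lehmann upper 95% limit lies below 24 h gave the same decision as the shifted test in 400 of 400 simulated data sets.

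**4. Size needed for 80% power under B with normal data.** The rank test's relative efficiency is 3/π, so 83.04 / (3/π) = 86.96, or 87 per arm. Simulated power at 87 was 79.8%.

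**The case against.** The strongest reply is that the line should be read with its neighbours. It speaks of assessing noninferiority, Section 2.1 gives direction and limit, and Section 6.1 pairs 24 h with an alpha. On that reading a rank test against 24 h is the natural meaning, and p > 0.05 as success is an invention. It is fair that the plan nowhere adopts reading A, and its error rates are illustrative only. But a natural reading is not a rule, and even a generous reader cannot recover the interval level, because the sample size and the stated alpha disagree.

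Second, the normal-data figure is the least realistic. Stays cannot be negative, and with SD 55.2 h a normal model puts about 14% of them below zero at a mean of 60 h. At that mean, lognormal data make reading A stricter than the nominal 2.5%. This stands, and it shows that reading A's error rate is set by an unknown distribution and not by design.

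Third, the shifted test's good behaviour depends on a pure location shift. If amlodipine instead lengthened stays proportionally (lognormal, same coefficient of variation, true mean excess 24 h), the proposed rule would declare noninferiority in roughly 4% to 28% of trials over the same control means. Reading A would do so in 25% to 36%. This too stands as a limit on interpretation: a bound on the shift does not bound the difference in means. The proposed rule therefore has to state that the 24 h applies to the shift.

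**Conclusion.** The concern holds and must be fixed before any analysis. The documents contain a limit and a test, but nothing that connects them and no success rule. This is a gap in specification; the rank-sum method itself is usable.

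The size depends on what the sponsor would otherwise do. If non-significance were taken as success, the false noninferiority rate at a true 24 h excess could lie anywhere from 0.5% to 32% over the cases examined, against 2.2% to 2.6% for the shifted test. With normal data and truly equal stays, the two readings would disagree on the same data in 30% of trials at 66 per arm and 22% at 80. These figures assume SD 55.2 h in both arms, a pure location shift and, for lognormal data, the assumed control means. That no success rule is stated depends on none of these assumptions.

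**What to change.** Replace the synopsis line, and repeat the text in Section 6:

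> The difference in length of stay (amlodipine minus nifedipine ER) will be estimated by the Hodges-Lehmann location shift with its rank-based two-sided 95% confidence interval. The 24 h limit applies to this shift; noninferiority is concluded if the upper limit is below 24 h. A non-significant unshifted rank-sum test is not evidence of noninferiority.

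This keeps the rank method that the synopsis names, and the 95% level follows the two-tailed 0.05 in Section 6.1. If one-sided 0.05 was intended, as the 66 per arm suggests, the sponsor should say so and use a 90% interval in both places.

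Restate the power in Section 6.1 for whichever rule is adopted. The text itself costs three sentences, with the same data and software. The real cost is power at the 95% level: with normal data and no true difference, 68% at 66 per arm and 76% at 80, with about 87 per arm needed for 80%. If stays are lognormal, power at 80 per arm is about 86% or more over the control means examined. The proposed text does not use the stratification by chronic hypertension in Section 3.2, which may leave the interval wider than necessary.
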